Buspirone for Functional Dysphagia - Protocol

Introduction

Functional Dysphagia has been defined by the Rome Criteria as a syndrome in which patients report symptoms of dysphagia without evidence of GERD and without any histopathology-based esophageal motility disorder. (Rome Criteria) Ineffective Esophageal Motility is a manometric diagnosis (based on the Chicago Classification) without a histopathology correlate which has been shown to cause dysphagia. (Kahrilas, PJ) Data related to treatment of this disorder are limited. Buspirone is a serotonin modulating anxiolytic and antidepressant medication with a reliable safety profile, which has been shown to improve esophageal motility. (Blonski W) We plan to perform a prospective randomized double-blind crossover style placebo controlled trial of the effect of buspirone on patients with functional dysphagia and ineffective esophageal motility.

Background and Significance

Functional Dysphagia has been defined by the Rome Criteria as a syndrome in which patients report symptoms of dysphagia without evidence of GERD and without any histopathology-based esophageal motility disorder. (Rome Criteria) Ineffective Esophageal Motility (IEM) is a manometric diagnosis (based on the Chicago Classification) without a histopathology correlate which has been shown to cause dysphagia. (Kahrilas, PJ)

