
Study Design

Methods

Randomized Double-Blind Crossover Placebo controlled prospective trial

Sample

Inclusion Criteria: >18 years old, diagnosis of IEM, negative EGD or barium swallow, biopsies negative for EOE Exclusion Criteria: Have not had any changes to serotonin modulating medications over the last 6 weeks This is a cross-over style study and all participants will be both studied in the treatment and control arms.

NCT: 02674412

Version Date: 08/10/2016

Previous studies have shown up to a 100% improvement in baseline manometric findings in patients treated with buspirone. We hope to show at least a 25% difference with a p<0.05 and power 0.8. To show this effect, we will need 15-20 patients (depending on the standard deviation of the specific marker being tested).

Research Procedures – Define the data to be collected to answer the hypothesis/research question(s)

Nurses at the Swallowing Center facilitate the final read by a licensed physician of all manometries performed here. For every patient diagnosed with functional dysphagia and IEM who meets the inclusion and exclusion criteria, the nurses will notify the investigators. Review of electronic charts for all patients undergoing manometry is part of the routine medical practice and responsibility of the nurses. The nurses will also seek the patient's permission to be contacted to hear about the details of an ongoing study related to their diagnosis.

Once the investigators are notified of this diagnosis, one of the investigators will contact the patient to discuss the logistics of the study as well as obtain informed consent. After informed consent is obtained, patients will be randomized to either group A or group B. Both patients and investigators will be blinded to the assignment. All patients will be administered a Mayo Dysphagia Questionnaire as well as a validated GERD questionnaire. Subsequently, all patients in Group A will receive placebo and Group B will receive buspirone administered by pharmacy.

After two week of treatment, all patients will undergo repeat administration of questionnaires as well as assessment of side effects. They will also undergo repeat manometry. All participants will be reimbursed with \$100 for travel expenses.

Subsequently, all patients will be treatment free for a washout period of two weeks.

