Patients in Group A will then be treated with buspirone and Group B will be treated with placebo for two weeks followed by repeat questionnaires and manometry. All participants will be reimbursed with another \$100 for travel expenses.

All participants will be contacted by phone one week after they start their treatments to assess for tolerability and side effects related to the medication.

The two interventions that are part of the study are buspirone as well as the two subsequent manometries. Both costs will be incurred by the investigators.

Data Analysis

Descriptive statistics will be computed for all variables. This includes means, standard deviation and percentiles for continuous variables and frequencies and percentages for categorical factors the t test and odds ratio will be calculated for comparison. All analyses will be performed using SAS (version 9.2, The SAS Institute, Cary, NC). The analysis will be completed by one of the investigators.

Adverse Events and Data Monitoring Committee(DMC)

This project does not require an independent DMC or DSMB because this is an open-label intervention looking solely at symptom/sign changes related to buspirone.

After two weeks of being on the medication, each patient will be questioned about his/her baseline symptoms, new symptoms, and any side effects related to the medications (specifically the common side effects of buspirone). All Adverse Events will be reported to the IRB using the Adverse Event Form.

Consent

The consent interview will take place in private patient rooms at the Swallowing Center.

The consent interview will take place after patients are diagnosed with functional dysphagia or IEM. One of the investigators will discuss the study in detail and answer all questions. The patients will then be provided the opportunity to sign the consent or take time to think about the study before signing or rejecting the study.

The consent will be documented on the informed consent form attached with the application.

NCT: 02674412

Version Date: 08/10/2016

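### Does describing the trial as open-label in the no-DMC statement leave safety review without a sound basis?

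*Combined protocol and SAP*

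**What the plan says.** The section on adverse events and data monitoring states that the project "does not require an independent DMC or DSMB because this is an open-label intervention looking solely at symptom/sign changes related to buspirone". That sentence offers two grounds: that the intervention is open-label, and that only changes in symptoms and signs are studied.

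Elsewhere the design is described differently. The Introduction plans a "prospective randomized double-blind crossover style placebo controlled trial", and the Methods line under Study Design repeats this. Research Procedures adds: "Both patients and investigators will be blinded to the assignment". In the first period, "all patients in Group A will receive placebo and Group B will receive buspirone administered by pharmacy". After the washout the treatments are exchanged, and "Group B will be treated with placebo for two weeks followed by repeat questionnaires and manometry".

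On safety, the Introduction calls buspirone a "medication with a reliable safety profile". Participants are telephoned one week after starting each treatment. The adverse-events section adds: "After two weeks of being on the medication, each patient will be questioned". It also says: "All Adverse Events will be reported to the IRB using the Adverse Event Form". These sentences do not name who collects or reports the events. No code-break procedure is described, and no reviewer of events by treatment is named.

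**The concern.** The word open-label follows a because, so it reads as a stated reason for a decision about safety oversight, and it is false for this design. In an open-label trial, whoever records an event can relate it at once to drug or placebo. Under the blind set out in Research Procedures, investigators cannot. Pharmacy supplies the treatment but has no stated part in handling adverse events. The protocol does not say whether the form sent to the IRB shows treatment.

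Two harms could follow. If the blind is kept, nobody during the trial may be placed to see an excess of events on buspirone. If staff instead take the word open-label at face value and learn the assignments, the blind that protects the questionnaire and side-effect comparisons is lost.

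**Working it through.** **1. Is the contradiction real?** Yes. The Introduction and the Methods say double-blind, Research Procedures blinds patients and investigators, and no open-label phase is described. Only the no-DMC sentence says open-label.

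**2. Which statement governs?** The design is named as double-blind in two places. A third states who is blinded, and the placebo and group structure carries it out. Against this stands one adjective in an administrative paragraph. Staff following the procedures would keep the blind.

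**3. Did the no-DMC decision depend on knowing the treatment?** The protocol never says so. It does not say that investigators will relate events to buspirone or placebo as they occur. That link is an inference from one word.

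**4. What can be seen under the blind?** Group A takes placebo then buspirone, and Group B the reverse. Write nA and nB for the group sizes, N for their sum, and pb and pp for the side-effect rates on buspirone and placebo. The protocol gives N as 15 to 20. The rates and the 1:1 split are assumptions, as are the absence of period or carryover effects and complete assessment.

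- By treatment: N × pb against N × pp.
- Period 1: nA × pp + nB × pb.
- Period 2: nA × pb + nB × pp.
- Period 2 minus period 1: (nA − nB) × (pb − pp), which is 0 when nA = nB.
- Pooled rate with all periods assessed: (pb + pp)/2.

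| N (A:B) | pp | pb | By treatment (buspirone v placebo) | By period (1 v 2) | Pooled rate |
|---|---|---|---|---|---|
| 20 (10:10) | 10% | 10% | 2 v 2 | 2 v 2 | 10% |
| 20 (10:10) | 10% | 30% | 6 v 2 | 4 v 4 | 20% |
| 20 (10:10) | 10% | 50% | 10 v 2 | 6 v 6 | 30% |
| 15 (8:7) | 10% | 30% | 4.5 v 1.5 | 2.9 v 3.1 | 20% |
| 15 (8:7) | 10% | 50% | 7.5 v 1.5 | 4.3 v 4.7 | 30% |

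Period counts therefore hide a drug effect. But none of these quantities contains the word open-label: delete it and every row is unchanged. The table describes blinding, not the slip.

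**5. Are pooled and period counts all that a blinded reviewer has?** No. Each patient's pair of periods is also visible. Assume events are independent within a patient. The chance of an event in exactly one period is pb(1 − pp) + pp(1 − pb).

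- 50% v 10%: 0.5 × 0.9 + 0.1 × 0.5 = 0.50, or 10 of 20 patients.
- 10% v 10%: 0.1 × 0.9 + 0.1 × 0.9 = 0.18, or 3.6 of 20.
- 30% v 30% (same pooled rate as the first): 0.3 × 0.7 + 0.3 × 0.7 = 0.42, or 8.4 of 20.

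The signal is weak, because most of the rise from 3.6 to 10 comes from the higher overall rate. Still, the blinded view is not empty.

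**6. Do the group letters break the blind?** The protocol states what A and B receive, so a visible letter would reveal the treatment. But it randomises patients to A or B and then blinds patients and investigators to the assignment. On a plain reading the assignment is the letter, so it is already withheld.

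**The case for a change.** The strongest argument for acting is that a false reason for a safety decision should not stand, least of all where nothing replaces it. The remaining ground does not make the first one true. It is also arguably narrower than the study, which includes manometry. No person is named as holding the code or as able to open it, and the analysis is assigned to one of the investigators, all of whom are blinded. Correcting this would take only a few words.

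The false word stands as an error, and so does the silence about the code. The argument does not show any consequence. The protocol does not name the investigators as the people who collect and report events; that is the natural reading of passive sentences. Whether the IRB form shows treatment cannot be judged, because the form is not in the document. That staff would override an express blinding instruction because of one adjective elsewhere is conjecture. Most importantly, blinded and pooled review would be acceptable in this trial, so removing the word could leave safety review exactly as it is now.

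**Conclusion.** This is a clerical slip together with a gap that trial staff fill in the ordinary way. The no-DMC sentence misdescribes the design, but the design and blinding statements are clear enough to settle how the trial is run. The documents do not show that a DMC is needed: the trial has 15 to 20 patients, two two-week treatment periods and a drug whose safety profile the Introduction calls reliable. The effect of the slip on the results is nil. It alters no estimate, loses no data and leaves no adverse event uncollected or unreported to the IRB.

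The expected counts (10 against 2 by treatment, 6 against 6 by period in the most extreme case) rest on assumed rates and equal allocation, and they measure the cost of blinding, which the protocol chose deliberately. Who holds the code and how it may be opened are operational details that are normally settled with pharmacy. Tidying the word when the document is next edited would be reasonable, but no change to the plan follows. This conclusion assumes that the blind is run as Research Procedures states and that the group letters are covered by it.

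### Symptoms overlapping buspirone's side effects are not recorded before either treatment period, so calling one new rests partly on recall

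*Combined protocol and SAP*

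**What the plan says.** Research Procedures sets the order of events in period 1. After consent and randomization, "All patients will be administered a Mayo Dysphagia Questionnaire as well as a validated GERD questionnaire". Dosing follows: "Subsequently, all patients in Group A will receive placebo and Group B will receive buspirone administered by pharmacy". At two weeks, "all patients will undergo repeat administration of questionnaires as well as assessment of side effects", together with repeat manometry. A two-week washout comes next, and then the crossed-over treatment "for two weeks followed by repeat questionnaires and manometry". No assessment is listed between the end of washout and the first dose of period 2.

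Two further places deal with tolerability. Research Procedures adds a call: "All participants will be contacted by phone one week after they start their treatments to assess for tolerability and side effects related to the medication". Separately, the Adverse Events and Data Monitoring Committee section says that after two weeks on the medication "each patient will be questioned about his/her baseline symptoms, new symptoms, and any side effects related to the medications", and singles out the side effects commonly seen with buspirone. I read this as applying at the end of both periods, although the description of period 2 lists only questionnaires and manometry.

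**The concern.** A side-effect comparison needs a way to tell symptoms that arose on treatment from those already present. For dysphagia and reflux the protocol has one, because the questionnaires are completed before dosing and repeated afterwards. For the other symptoms that the two-week interview covers, it has none. The side-effect items have no pre-dose counterpart in period 1, and no symptom is recorded after washout in period 2.

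Sorting such a symptom into new or pre-existing then depends on memory. A long-standing complaint remembered as new adds a false event. Under equal questioning this happens at about the same rate on both treatments, which pulls a ratio comparison toward no difference. The reverse error, a real event remembered as long-standing, loses information. In Group B, a symptom that began on buspirone and was still present after washout could be filed as pre-existing or as new on placebo, and no record would settle which.

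What is at stake is the tolerability comparison. The side-effect interview and the one-week call are the only safety assessments specified, and with 15-20 patients one or two misfiled events per period are noticeable.

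**Working it through.** **Order of assessments.** The point turns first on the schedule, so the steps are set side by side.

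| Time | Dysphagia and GERD symptoms | Side-effect items |
|---|---|---|
| Before first dose, period 1 | Both questionnaires | Nothing specified |
| One week into treatment | Nothing specified | Phone call |
| End of period 1 (week 2) | Questionnaires repeated | Interview |
| End of washout (week 4), before period 2 | Nothing specified | Nothing specified |
| One week into period 2 | Nothing specified | Phone call |
| End of period 2 (week 6) | Questionnaires repeated | Interview, if the Adverse Events section covers both periods |

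Every entry in the last column falls after dosing has begun. The recall interval is two weeks in period 1. In period 2 it is two weeks if the reference is the start of that period, and 2 + 2 + 2 = 6 weeks if the reference is study entry. The protocol does not say which.

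**The plan's own figures.** The plan gives no side-effect rate and no target for a side-effect comparison, so there is nothing to reproduce. Its sample-size statement ("We hope to show at least a 25% difference with a p<0.05 and power 0.8", 15-20 patients) concerns manometric markers, gives no standard deviation, and has no bearing here.

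**Illustration of dilution.** All four inputs are assumptions; none comes from the documents.

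- True new-event rates per period: 20% on buspirone, 5% on placebo.
- Proportion with at least one listed symptom before dosing: 30%.
- Proportion of those who recall it as new: *r* = 10%, 25% or 50%.

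The false-event rate is *f* = 0.30 × *r*. If false and true events are independent, the recorded rate is 1 − (1 − true rate)(1 − *f*).

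True odds ratio: (0.20/0.80) / (0.05/0.95) = 0.25/0.0526 = 4.75.

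| *r* | *f* | Recorded, buspirone | Recorded, placebo | Recorded odds ratio |
|---|---|---|---|---|
| 10% | 0.03 | 1 − 0.80 × 0.97 = 22.4% | 1 − 0.95 × 0.97 = 7.9% | 0.2887/0.0852 = 3.4 |
| 25% | 0.075 | 1 − 0.80 × 0.925 = 26.0% | 1 − 0.95 × 0.925 = 12.1% | 0.3514/0.1380 = 2.55 |
| 50% | 0.15 | 1 − 0.80 × 0.85 = 32.0% | 1 − 0.95 × 0.85 = 19.3% | 0.4706/0.2384 = 2.0 |

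With 20 patients, the expected number with a false new symptom in each period is 20 × *f* = 0.6, 1.5 or 3.0. With 15 it is 0.45, 1.1 or 2.3.

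The distortion depends on the scale. The true difference in rates is 15 percentage points, and the recorded difference is 15 × (1 − *f*) = 14.6, 13.9 or 12.8 points. The odds ratio moves far more than the difference does.

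**The case against.** Several objections carry weight.

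- **Symptoms are recorded before dosing.** Read alone, the Adverse Events sentence might suggest that no baseline symptoms are captured until week two. Research Procedures rules that out, because both questionnaires precede the first dose and the week-two set is a repeat. The gap is confined to symptoms outside those two instruments, and to the start of period 2.
- **The baseline-symptom question need not be retrospective.** It can naturally mean the present state of the symptoms the patient came with. A reader who infers that patients must reconstruct their earlier state goes beyond the text. On the milder reading, however, non-esophageal symptoms have no baseline at all, so the gap remains.
- **There are other side-effect contacts.** The one-week call shortens recall of when a symptom began, and the end-of-period-1 interview gives period 2 some history. But the call takes place on treatment, and the end-of-period-1 record predates the washout. Neither shows the state just before a first dose.
- **The same questions are asked on both treatments, under blinding.** This protects against a spurious difference and limits the expected harm to dilution; it does not prevent dilution. The protection also assumes that blinding holds. The Adverse Events section calls the study open-label, while Research Procedures says patients and investigators are blinded.
- **A side-effect odds ratio is inferred.** Data Analysis names odds ratios for comparison without tying them to side effects. Nor does the protocol say that being new decides what is counted; all adverse events go to the IRB. The stated expectations concern motility, dysphagia and GERD, so this comparison is secondary.
- **A trial of this size could not establish the difference anyway.** With 20 patients the assumed true rates give 4 events against 1. Even with perfect recording, an unpaired Fisher test gives p of about 0.34, and an exact McNemar test gives 0.25 to 0.375 depending on overlap. One may be tempted to say that recall error would hide a real tolerability difference, but on these inputs sample size already does that. What remains is a less accurate descriptive comparison.

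**Conclusion.** The point holds as a modest gap in safety data collection. The protocol specifies no pre-dose record of the side-effect items for period 1 and no symptom record after washout for period 2, so deciding that a non-esophageal symptom is new rests partly on recall.

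The likely effect is dilution of a secondary, descriptive buspirone-placebo comparison. Its size cannot be derived from the documents. The fall in the odds ratio from 4.75 to between about 3.4 and 2.0 depends entirely on the assumed rates, on independence of false and true events, and on recall error being equal on both treatments. The opposite error, real events recalled as pre-existing, has not been quantified.

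The documents do not support inferring that efficacy is compromised. Manometry does not depend on this interview, and the dysphagia and GERD questionnaires have their own pre-dose administration. The case for a change is that prospective recording is plainly better than sorting symptoms afterwards, and costs very little.

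**What to change.** Add to Research Procedures that the side-effect checklist used at two weeks is also given with the entry questionnaires, before the first dose, and again just before the first dose of period 2, by phone if no visit is planned.

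Add to the Adverse Events section that a symptom counts as treatment-emergent in a period if it was absent or less severe on the record taken immediately before that period. State there that the interview applies at the end of both periods.

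Keep the two-week question on baseline symptoms, but say that it asks for their current status. Removing it is not justified, because it is a legitimate part of the safety interview.

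The cost is a few minutes per patient at entry, one brief contact before period 2, and a few sentences of protocol text. No new procedure is needed.
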